3.2 Exclusion criteria

Patients should not enter the study if any of the following exclusion criteria are fulfilled:

1. * Involvement in the planning and/or conduct of the study (applies to AstraZeneca staff and/or staff at the study site).
2. Cytotoxic chemotherapy, hormonal or non hormonal targeted therapy within 21 days of Cycle 1 Day 1 is not permitted. Palliative radiotherapy must have been completed 21 or more days before Cycle 1 Day 1. The patient can receive a stable dose of bisphosphonates or denosumab for bone metastases, before and during the study as long as these were started at least 5 days prior to study treatment.
3. * More than 2 prior lines of cytotoxic chemotherapy for metastatic disease.
 - Prior treatments with hormonal therapy and non hormonal targeted therapy are allowed and not counted as a prior line of cytotoxic chemotherapy.
 - For the purposes of this protocol, the combination of an aromatase inhibitor and everolimus is not considered cytotoxic chemotherapy.
 - Treatment with biologics will not be considered as prior line of therapy.
4. * Previous randomisation in the present study.

5. * Previous treatment with a PARP inhibitor (including olaparib) or other DDR inhibitor (unless treatment was for less than 3 weeks duration and at least 12 months have elapsed between the last dose and randomisation. Patients that did not tolerate prior treatment are excluded).
6. * Exposure to a small molecule IP within 30 days or 5 half-lives (whichever is longer) prior to randomisation. The minimum washout period for immunotherapy shall be 42 days.
7. * Patients with MDS/AML or with features suggestive of MDS/AML.
8. * Patients with second primary cancer, EXCEPTIONS: adequately treated non melanoma skin cancer, curatively treated in-situ cancer of the cervix, Ductal Carcinoma in Situ (DCIS), stage 1 grade 1 endometrial carcinoma, or other solid tumours curatively treated with no evidence of disease for ≥ 5 years prior to study entry (including lymphomas [without bone marrow involvement]).
9. Mean resting corrected QTc interval using the Fridericia formula (QTcF) >470 msec/female patients and >450 msec for male patients (as calculated per institutional standards) obtained from 3 ECGs performed 2-5 minutes apart at study entry, or congenital long QT syndrome.

No longer applicable from CSPv6.0 AZD1775 should not be given to patients who have a history of Torsades de pointes unless all risk factors that contributed to Torsades have been corrected. AZD1775 has not been studied in patients with ventricular arrhythmias or recent myocardial infarction.

10. Any of the following cardiac diseases currently or within the last 6 months
 - Unstable angina pectoris
 - Congestive heart failure \geq Class 2 as defined by the New York Heart Association (see [Appendix F](#))
 - Acute myocardial infarction
 - Conduction abnormality not controlled with pacemaker or medication (patients with a conduction abnormality controlled with pacemaker or medication at the time of screening are eligible)
 - Significant ventricular or supraventricular arrhythmias (patients with chronic rate-controlled atrial fibrillation in the absence of other cardiac abnormalities are eligible)

11. Concomitant use of known strong cytochrome P (CYP) 3A inhibitors (eg. itraconazole, telithromycin, clarithromycin, protease inhibitors boosted with ritonavir or cobicistat, indinavir, saquinavir, nelfinavir, boceprevir, telaprevir) or moderate CYP3A inhibitors (eg. ciprofloxacin, erythromycin, diltiazem, fluconazole, verapamil). The required washout period prior to starting study treatment is 2 weeks.

No longer applicable from CSPv7.0 Patient has had prescription or non-prescription drugs or other products known to be sensitive CYP3A4 substrates or CYP3A4 substrates with a narrow therapeutic index, or to be moderate to strong inhibitors/inducers of CYP3A4 which cannot be discontinued 2 weeks prior to Day 1 of dosing and withheld throughout the study until 2 weeks after the last dose of study drug (see [Appendix H](#)).

No longer applicable from CSPv7.0 Transporter studies (*in vitro*) have shown that AZD1775 is an inhibitor of breast cancer resistance protein (BCRP). Please refer to [Appendix H](#) for use with BCRP substrates.

No longer applicable from CSPv7.0 Patients should stop using herbal medications 7 days prior to first dose of study treatment. Please see [Appendix H](#) for further details.

12. Concomitant use of known strong (eg. phenobarbital, enzalutamide, phenytoin, rifampicin, rifabutin, rifapentine, carbamazepine, nevirapine and St John's Wort) or moderate CYP3A inducers (eg. bosentan, efavirenz, modafinil). The required washout period prior to starting study treatment is 5 weeks for enzalutamide or phenobarbital and 3 weeks for other agents.
13. Persistent toxicities (\geq CTCAE grade 2) caused by previous cancer therapy, excluding alopecia and CTCAE grade 2 peripheral neuropathy.
14. Major surgery within 2 weeks of starting study treatment: patients must have recovered from any effects of any major surgery.
15. * Immunocompromised patients, eg, patients who are known to be serologically positive for human immunodeficiency virus (HIV).
16. * Patients with known active hepatitis (ie, hepatitis B or C).
17. * Patients considered a poor medical risk due to a serious, uncontrolled medical disorder, non malignant systemic disease or active, uncontrolled infection.
- Examples include, but are not limited to, uncontrolled ventricular arrhythmia, recent (within 3 months) myocardial infarction, uncontrolled major seizure disorder, unstable spinal cord compression, superior vena cava syndrome, extensive interstitial bilateral lung disease on High

Resolution CT scan or any psychiatric disorder that prohibits obtaining informed consent, and any other medical condition that, in the opinion of the Investigator, places the patient at unacceptable risk of toxicity.

18. * Patients with symptomatic uncontrolled brain metastases.
 - A scan to confirm the absence of brain metastases is not required. Patients with spinal cord compression unless considered to have received definitive treatment for this and evidence of clinically stable disease (SD) for 28 days.
 - * Patients with a history of treated central nervous system (CNS) metastases are eligible, provided they meet all of the following criteria: Disease outside the CNS is present. No clinical evidence of progression since completion of CNS-directed therapy. Minimum of 3 weeks between completion of radiotherapy and Cycle 1 Day 1 and recovery from significant (Grade ≥ 3) acute toxicity with no ongoing requirement for >10 mg of prednisone per day or an equivalent dose of other corticosteroid. If on corticosteroids, the patient should be receiving a stable dose of corticosteroids, started at least 4 weeks prior to treatment.
19. * Patients unable to swallow orally administered medication and patients with gastrointestinal disorders likely to interfere with absorption of the study medication.
20. * Patients with a known hypersensitivity to olaparib, AZD1775, ceralasertib, or any of the excipients of the products.
21. Pregnant or breast feeding women.

Procedures for withdrawal of incorrectly enrolled patients see Section 3.4.

3.3 Patient enrolment and randomisation

Investigator(s) should keep a record, the screening log, of patients who entered pre-study screening.

The Investigator(s) will:

1. Obtain signed informed consent from the potential patient before any study specific procedures are performed.
2. Assign potential patient a unique enrolment number, beginning with 'E#'.
E#
3. Determine patient eligibility. See Section 3.1 and 3.2.

If a patient withdraws from participation in the study, then his/her enrolment/randomisation code cannot be reused.

Randomisation codes will be assigned strictly sequentially as patients become eligible for randomisation.

3.3.1 Lynparza HRR Assay

AstraZeneca has partnered with FMI to develop a novel tumour tissue-based companion diagnostic – the Lynparza HRR assay – for the detection of mutations in a panel of 15 HRR genes. FMI will provide the CTA, a novel NGS-based assay that will be performed as a single laboratory testing service using DNA extracted from FFPE tumour tissue. The tumour sample will be tested for qualifying mutation in **CCI** HRR genes simultaneously: **CCI**

. The Lynparza HRR Assay will be based on Foundation Medicine's NGS assay platform (DX1 bait set) for cancer gene profiling. This DX1 bait set covers exons from 310 genes and introns from 35 genes.

All patients must provide a tumour sample that meets the tissue specifications outlined in the laboratory manual, for central tissue testing by FMI using the Lynparza HRR assay. For each patient that passes tissue sample and sequencing quality control, FMI will generate a report specifying the presence or absence of a qualifying mutation in the HRR genes. A qualifying mutation is regarded as deleterious or suspected deleterious if it results in protein truncation (which includes nonsense, frameshift, or consensus splice site mutations), or select missense mutations well known to be deleterious in certain genes (such as *BRCA1*, *BRCA2*) in ClinVar/BIC databases.

3.4 Procedures for handling incorrectly enrolled or randomised patients

Patients who fail to meet the eligibility criteria should not, under any circumstances, be enrolled or receive study medication. There can be no exceptions to this rule. Patients who are enrolled, but subsequently found not to meet all the eligibility criteria must not be randomised or initiated on treatment, and must be withdrawn from the study.

Where a patient does not meet all the eligibility criteria but is randomised in error, or incorrectly started on treatment, the Investigator should inform the AstraZeneca study physician immediately, and a discussion should occur between the AstraZeneca study physician and the Investigator regarding whether to discontinue the patient from treatment where required by local law/ local requirements or to continue the study treatment in the best interest of the patient. The AstraZeneca study physician must ensure all decisions are appropriately documented.

3.5 Methods for assigning treatment arms

Eligible patients will be randomised by a ratio 1:1:1 to olaparib monotherapy, ceralasertib+olaparib or AZD1775+olaparib combinations. AZD1775+olaparib arm was closed in April 2019 so randomisation ratio will be 1:1 to olaparib monotherapy or ceralasertib+olaparib. The actual treatment given to individual patients will be determined by

a randomisation scheme that has been loaded into the Interactive Voice Response System/Interactive Web Response System (IVRS/IWRS) database.

The process for randomisation and associated Investigator tasks will be outlined in the IxRS manual.

A blocked randomisation list will be generated at PAREXEL Informatics in accordance with AZ Rand. The randomisation scheme will be stratified based on the

- tumour biomarker strata A, B, C defined in Section 1.4
- patient's prior platinum-based therapy (no / yes)

Randomisation in all centres through IxRS will minimise any imbalance in the total number of patients assigned to each treatment arm. The randomisation list will be loaded into the Interactive Response Technology (IRT) system.

Patient eligibility will be established before treatment randomisation. Once the eligibility of a patient has been confirmed, the Investigator (or nominated assistant) should contact the IRT system for allocation of randomised study treatment. The IRT system will inform the Investigator of the Kit identification (ID) number to be allocated to the patient at the randomisation visit. The Investigator will call/log in to the IRT system for each subsequent dispensing visit for assignment of a new Kit ID number. The Kit ID number dispensed at each visit will correspond to the study treatment to which the patient was originally randomised.

It is recommended that patients commence study treatment as soon as possible after randomisation, and ideally within 3 days.

If a patient discontinues participation in the study, then their enrolment/randomisation code cannot be reused.

Once 75 non *HRRm* patients have been recruited, recruitment into this stratum will be paused while the interim futility analysis is conducted. Similarly, if an interim futility analysis is necessary for the non *BRCAm* *HRRm* stratum, recruitment to stratum B will be paused until the analysis is complete.

3.6 Methods for ensuring blinding

Given the study treatment design (monotherapy and 2 different combination therapies will be employed; monotherapy and 1 combination from April 2019) neither patients nor Investigators will be blinded to study treatment. However, to limit bias on study conduct, data quality, data analyses and data interpretation, appropriate key personnel and certain functions at the Sponsor will remain blinded to treatment allocation until general unblinding of each stratum. Separate unblinded counterparts, e.g. biostatisticians and statistical programmers will do all necessary unblinded work during the course of the study, including the interaction with

the AZ ISRC and URC. Detailed procedures for maintenance of the blind will be described in a Blinding Maintenance Plan.

3.7 Restrictions

3.7.1 Grapefruit juice and Seville oranges

For all patients, it is prohibited to consume grapefruit juice or Seville oranges (including marmalade, juice, etc.) while participating in the study.

3.7.2 Contraception

Women of childbearing potential and their partners, who are sexually active, must agree to the use of TWO highly effective forms of contraception in combination. This should be started from the signing of the informed consent and continue throughout the period of taking study treatment and for at least 1 month after last dose of study drug(s), or they must totally/truly abstain from any form of sexual intercourse.

Male patients must use a condom during treatment and for 6 months after the last dose of study drug(s) when having sexual intercourse with a pregnant woman or with a woman of childbearing potential. Female partners of male patients should also use a highly effective form of contraception if they are of childbearing potential. Male patients should not donate sperm throughout the period of taking study drug(s) and for 6 months following the last dose of study drugs.

Male patients will be advised to arrange for the freezing of sperm samples prior to the start of the study should they wish to father children while on the study or during the 6 months after stopping study treatment.

For details of acceptable methods of contraception refer to [Appendix E](#) Acceptable Birth Control Methods.

3.7.3 Sun Exposure

Precautions are advised as a lifestyle recommendation when outside in the sun e.g. limiting the duration of sun exposure, wearing protective clothing (hat and sunglasses) and sunscreen.

3.8 Discontinuation of IP

Patients may be discontinued from IP in the following situations:

- Patient decision. The patient is free, at any time, to discontinue treatment, without prejudice to further treatment.
- AE
- Severe non compliance with the Clinical Study Protocol
- Bone marrow findings consistent with MDS/AML

- Objective progression (based on Investigator assessment) according to RECIST 1.1 criteria (unless in the Investigator's opinion the patient is benefiting from the treatment and does not meet any other discontinuation criteria as outlined in Section 3.9 and Section 3.10).
- Development of any study specific criteria for discontinuation (see Section 3.9 and Section 3.10)
- Unacceptable toxicity (patients can temporarily discontinue IP due to toxicity; IP can be re-started provided the disease has not progressed since discontinuation)
- A positive pregnancy test

3.8.1 Procedures for discontinuation of a patient from IP

At any time, patients are free to discontinue IP or withdraw from the study (ie, IP and assessments – see Section 3.9), without prejudice to further treatment. A patient that decides to discontinue IP will always be asked about the reason(s) and the presence of any AEs. If possible, they will be seen and assessed by an Investigator(s). Adverse events will be followed up (See Section 6); CCI (eg, for CCI) and all study drugs should be returned by the patient.

By discontinuing from study treatment, the patient is not withdrawing from the study. Patients should be followed for progression (if discontinuation in the absence of progression) and OS following treatment discontinuation as per the protocol schedule.

A patient can discontinue one of the combination drugs for up to 28 days. However, if they need to discontinue one of the combination drugs permanently, they will have to discontinue both combination drugs permanently. Following the ISRC meeting on 17 April 2019 a recommendation was made to close the AZD1775+olaparib treatment arm across all biomarker strata and that patients currently receiving treatment with AZD1775+olaparib treatment be offered the opportunity to continue treatment of olaparib monotherapy at the approved dose (300 mg bd). Any patient discontinuing IP should be seen at 30 days post discontinuation for the evaluations outlined in the study schedule. The patient's tumour status should be assessed clinically and, if appropriate, disease progression should be confirmed by radiological assessment. After discontinuation of study medication, the Principal Investigator (PI)/Sub-Investigator will perform the best possible observation(s), test(s) and evaluation(s) as well as give appropriate medication and all possible measures for the safety of the patient. In addition, they will record on the electronic Case Report Form (eCRF) the date of discontinuation, the reasons, manifestation and treatment at the time of discontinuation. If patients discontinue study treatment, the Study Monitor must be informed immediately. Patients will be required to attend the treatment discontinuation visit. The patient should return all study medication.

Any AEs that are unresolved at the patient's last AE assessment in the study are followed up by the Investigator for as long as medically indicated, but without further recording in the

CRF. AstraZeneca retains the right to request additional information for any patient with ongoing AE(s)/SAE(s) at the end of the study, if judged necessary. Patients should be seen at least 30 days after discontinuing study medication to collect and/or complete AE information. For guidance on reporting AEs after the 30-day follow up period see Section 6.3.1.1.

Any patient who has not yet shown objective radiological disease progression at withdrawal from IP should continue to be followed as per RECIST 1.1.

All patients must be followed for survival, up to the final OS analysis (i.e. when OS data for the ceralasertib+olaparib vs. olaparib monotherapy pairwise comparison is approximately 70% mature).

If a patient is withdrawn from study, see Section 3.9.

3.9 Criteria for withdrawal from the study

Reasons for withdrawal from the study:

- Voluntary withdrawal by the patient who is at any time free to discontinue their participation in the study, without prejudice to further treatment.
- Incorrectly enrolled patients i.e. the patient does not meet the required inclusion/exclusion criteria for the study. If the patient has already been treated, the decision to withdraw will be made in the best interest of the patient by the Investigator and sponsor, in accordance with local law/ local requirements.
- Patient lost to follow-up.
- Death.

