5.1 Efficacy assessments

5.1.1 CT and MRI scans; Tumour assessments (RECIST 1.1)

Following the baseline assessment, subsequent tumour assessments according to RECIST 1.1 should be performed every 8 weeks (± 1 week) for the first 72 weeks and then every 12 weeks (± 1 week) thereafter, relative to the date of randomisation and irrespective of treatment decisions, up to objective disease progression by RECIST 1.1.

The imaging modalities used for RECIST 1.1 assessment will be CT scans of the chest, abdomen and pelvis (or MRI where CT is contraindicated) with other regions as clinically indicated for the assessment of disease. Brain CT scan/MRI at baseline should be done for patients with known history of brain metastatic disease. Any other sites at which new disease is suspected should also be appropriately imaged. The methods of assessment of tumour burden used at baseline must be used at each subsequent follow-up assessment.

Radiological examinations performed in the conduct of this study should be retained at site as source data.

Coded copies of all scans, regardless of modality, are to be sent to an AstraZeneca appointed CRO for BICR.

All treatment decisions will be based on site assessment of scans. After the primary PFS analysis for each of the strata, central review of scans will no longer be required for that stratum and Investigators will be advised when to stop sending copies of the scans to the CRO conducting the central review. Patients who are determined to have progressed according to RECIST 1.1 criteria by the Investigator will have scans centrally reviewed for confirmation of objective disease progression. If disease progression is not confirmed at central review an additional RECIST 1.1 assessment may be requested preferably at the next scheduled RECIST 1.1 visit, if the central assessment is available in an appropriate timeframe.

It is important to follow the assessment schedule as closely as possible. If scans are performed outside of scheduled visit ± 1 week window interval and the patient has not progressed, every attempt should be made to perform the subsequent scans at their scheduled time points. Patients will be evaluated until objective radiological disease progression by RECIST 1.1 as per the study schedule (see [Table 3](#), and [Table 4](#) and [Table 5](#)), and then followed for survival, regardless of whether study treatment is discontinued or delayed and/or protocol violations, unless they withdraw consent.

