8.3 Definitions of analysis sets

8.3.1 Full analysis set

The full analysis set (FAS) will include all randomised patients with treatment groups assigned in accordance with the randomisation, regardless of the treatment actually received. Patients who were randomised but did not subsequently receive treatment are included in the FAS. The analysis of data using the FAS therefore follows the principles of intent to treat (ITT). All efficacy and **CCI** data will be summarised and analysed using the FAS. Disposition, demographic data, baseline characteristics, etc will be summarized using the FAS.

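### Section 3.9 allows a randomised patient found ineligible to be withdrawn from the study, and so possibly from scans, in conflict with Sections 3.4 and 5.1.1

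*Protocol*

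**What the plan says.** Five parts of the protocol bear on a patient who is randomised and later found not to meet the entry criteria.

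- **Section 3.9** gives incorrect enrolment as a reason for withdrawal from the study. It covers patients who have started treatment: "If the patient has already been treated, the decision to withdraw will be made in the best interest of the patient by the Investigator" and the sponsor, in accordance with local law or requirements.
- **Section 3.8.1** describes what such withdrawal means and points to 3.9: "patients are free to discontinue IP or withdraw from the study (ie, IP and assessments". It keeps this apart from stopping the drug: "By discontinuing from study treatment, the patient is not withdrawing from the study".
- **Section 3.4** deals with the patient randomised in error. The investigator and the sponsor's study physician hold a discussion "regarding whether to discontinue the patient from treatment where required by local law/ local requirements or to continue the study treatment". Withdrawal from the study is required there only for patients enrolled but not yet randomised.
- **Section 5.1.1** says that patients are scanned until progression and then "followed for survival, regardless of whether study treatment is discontinued or delayed and/or protocol violations, unless they withdraw consent".
- **Section 8.3.1** keeps every randomised patient in the full analysis set (FAS): "Patients who were randomised but did not subsequently receive treatment are included in the FAS".

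Under Section 3.6, neither patients nor investigators are blinded, while certain sponsor functions are.

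**The concern.** The protocol separates leaving treatment from leaving the study, and 3.9 uses the second term for ineligibility. A site that follows 3.9 together with 3.8.1 could stop scanning a patient whom 5.1.1 says must be scanned. That patient remains in the FAS. PFS would then be censored at the last evaluable scan or, if there is none, at day 0 in the protocol (Study Day 1 in the SAP).

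Patients who fail entry criteria (for example on organ function or number of prior lines) are unlikely to be a random sample with respect to prognosis. The investigator who shares the decision knows the arm. Censoring that arises this way can be informative and can differ between arms, which weakens the intention-to-treat reading of the primary PFS comparison. No planned analysis benefits from ending follow-up, since the SAP (Section 2.2) has no per-protocol set.

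**Working it through.** **1. The passages side by side, for a patient already randomised**

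- Is withdrawal from the study an option? 3.9: yes, expressly for treated patients. 3.4: not mentioned; only treatment is discussed.
- Do scans continue? 3.8.1 read with 3.9: study withdrawal covers assessments. 5.1.1: yes, with withdrawn consent as the only exception.
- Is the patient analysed? 8.3.1: yes.

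The instruction in 3.9, taken with the gloss in 3.8.1, cannot be followed at the same time as 5.1.1.

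**2. Do the planned analyses repair a loss?** The attrition-bias analysis (SAP Section 4.2.5) puts back events that were observed after missed assessments. It cannot put back a progression that was never imaged. The reversed-censoring plot and the premature-censoring summary in the same section, and the listing of important deviations by arm (SAP Section 2.2), would show an imbalance but not correct it.

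**3. The plan's own figure.** Inputs from Protocol Section 8.2: hazard ratio (HR) 0.55, two-sided 10% level, 80% power. The sized comparison is 1:1. By Schoenfeld's formula:

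d = 4(z₀.₉₅ + z₀.₈₀)² / (ln HR)² = 4(1.645 + 0.842)² / (0.598)² ≈ 69.2, rounded up to 70, against 68 stated.

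Power at 68 events = Φ(½√68 × 0.598 − 1.645) = Φ(0.82) = 79.4%, against 80% stated. The figure reproduces. Maturity is 68/100 = 68%, as stated.

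**4. Events at stake.** One patient is 1/50 = 2% of an arm within a stratum. The documents give no ineligibility rate. Assuming 3 to 5 of about 100 are withdrawn before an event, at the average event probability: 3 × 0.68 = 2.0 and 5 × 0.68 = 3.4 events.

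**5. Power.** With k patients lost and no delay to the cut-off, expected events are 68 − 0.68k. To wait for 68 events, the others must reach a maturity of 68/(100 − k).

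| k (assumed) | Events, no delay | Power | Maturity needed to reach 68 |
|---|---|---|---|
| 2 | 66.6 | 78.7% | 69.4% |
| 5 | 64.6 | 77.6% | 71.6% |
| 10 | 61.2 | 75.6% | 75.6% |

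The analysis is triggered by events, so the trial can wait. Power is not the main issue.

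**6. Bias, worst case by construction.** The simulation assumes no true effect, 50 per arm, exponential PFS with median 5 months, 68% maturity and 8000 runs. In the combination arm only, the k patients next to progress are censored at about 8 weeks.

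| k | Mean HR estimate | One-sided false-positive rate (nominal 5%) |
|---|---|---|
| 0 | 1.00 | 5.1% |
| 1 | 0.97 | 6.4% |
| 2 | 0.94 | 8.4% |
| 5 | 0.86 | 15.5% |

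This shows how far a few perfectly selected losses could move the result. It is not a forecast.

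**The case against.** The best defence is that the protocol, read as a whole, already gives the answer. Section 3.2 ends by sending the reader to 3.4 for the withdrawal of incorrectly enrolled patients. Section 3.9 is a list of reasons, not an order. The mention of assessments in 3.8.1 sits in a sentence about what patients are free to do. No passage says in terms that a decision on ineligibility stops scans, and 5.1.1 is specific that they go on.

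Much of this stands, and it rules out several stronger readings that a reader might infer:

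- *That FAS patients will lose PFS follow-up.* The documents support only that they can. For treated patients the decision is case by case.
- *That an untreated randomised patient must be withdrawn.* A list of reasons does not say so, and 3.4 sends any patient randomised in error to a documented discussion.
- *That survival data are lost too.* Section 3.9.2 has sites check notes, hospital records, the general practitioner and death registries for withdrawn patients. A death within the allowed window still counts as a PFS event (Protocol Section 8.4.1, SAP Section 3.3.1).
- *That everyone deciding knows the arm.* The investigator does. Some sponsor functions are blinded, and whether the criteria were met is a fact fixed before randomisation.

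The defence does not remove the conflict. Section 3.9 expressly reaches treated patients, 3.8.1 attaches the end of assessments to study withdrawal and cross-refers to 3.9, and nothing states that 5.1.1 prevails.

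**Conclusion.** The inconsistency is real and should be resolved. As written, 3.9 permits the end of radiological follow-up for a randomised patient who stays in the primary analysis, on a decision shared by an unblinded investigator, and no planned analysis recovers the missing progressions. The consequence is a possibility of informative censoring that may differ by arm. It is not a demonstrated loss.

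The size is probably small. The figure of 2 to 3.4 events per stratum rests on an assumed 3 to 5 withdrawn patients per 100. It also takes every one of them to be withdrawn before an event, with no death counted in the window. The simulated false-positive rates also need one-sided, perfectly selected losses, so they are upper illustrations. The textual conflict depends on none of these figures.

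**What to change.** Reconcile 3.9 with 3.4 and 5.1.1 as follows.

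- Confine withdrawal from the study for ineligibility to patients not yet randomised.
- For a patient already randomised and found ineligible, state that the decision, in line with local law or requirements as now, concerns study treatment only and is made under 3.4.
- State that RECIST assessments and survival follow-up then continue as in 3.8.1 and 5.1.1, unless consent is withdrawn or local law requires follow-up to end.

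The treatment decision itself stays as 3.4 has it. No change to that rule is proposed.

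The cost is a short protocol amendment, with whatever approval Section 10.6 calls for, and continued scans for a few patients, which 5.1.1 already requires. The local-law wording must be kept, because the version history shows that 3.4 and 3.9 were revised to suit different regions.
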